6.4.3.2 Secondary Objectives Analyses

In secondary analyses, we will also analyze the following variables: Evaluation of ADHD subset IA and HI symptoms on AISRS, TASS 1 hour, 4 hours and 14-15 hours post dose: (total, inattentive and hyperactive-impulsive subsets) (for effects of Mydayis over time at different points of the day and within the day); expanded Adult ADHD Self Report Scale (ASRS) Symptom Checklist (total, inattentive and hyperactive-impulsive, executive function and emotional control subsets); symptoms of executive function (BRIEF-A: GEC, metacognition, behavioral regulation scales and subscales: Inhibit, Shift, Emotional Control, Initiate, Working Memory, Plan/Organize, Organization of Materials, Monitor); and neuropsychological tests (Stroop: Color, Word and Interference Score; and TOVA: Response Time Variability [RVP], Response Time, d', Errors of Omission, Errors of Commission, Post-Commission Response Times , Multiple Responses, Anticipatory Responses).

6.4.3.3 Safety/Pregnancy-related policy

Throughout this study, we will monitor safety and possible pregnancy by conducting safety clinical tests during screening and eligibility period. We will collect blood tests and urine test to ensure safe participation in the study. In addition, we will conduct the Columbia Suicide Severity Rating Scale (C-SSRS) to evaluate continued mental health and suicidality. We will monitor weekly vital signs (temperature, pulse, respiration, and blood pressure). Adverse events and concomitant medications will also be monitored. All

adverse events will be tabulated in manuscripts with significant testing using the appropriate general linear regression model.

We will report to Shire and our IRB within the necessary times. See section on adverse events. In addition, we will provide pregnant women with a pregnant woman contact sheet and pregnant woman ICF requesting permission to follow pregnant women to pregnancy outcome.

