	Week -3- 0 Screen	Week -3-0 Screen/BL	Week 1 PbO Lead in	Week 2 PbO Lead in	Week 1	Week 2	Week 3	Week 4	
Consent	x								
Demographics	x								
MINI	x								
ACDS v1.2	x								

AISRS	Х		Х	Х	Х	X	Х	Х	
CGI S	X		X	X	X	Х	X	X	
WEBNEURO; STROOP, GO/NO-GO, CONTINUOUS PERFORMANCE TEST CPT	Х			Х				х	
BRIEF A	Х			X				Х	
EXPANDED ASRS	X		X	X	Х	Х	X	X	
TASS		x	X	X	X	х	X	X	
Medical History		X							
Psychiatric History		x							
Physical Exam		X							

Hematology Chem, UA	X								
Drug Toxicology	Х								
Urine Pregnancy Test	Х								
ECG /EKG Reading	Х								
Review Eligibility		х							
Vital Signs w/ HT/WT	Х		Х	X	X	X	X	X	
C-SSRS		х	X	X	x	x	x	x	
Prior/Con Meds		х	Х	X	X	x	x	x	Х
Adverse Events		х	Х	X	X	X	X	X	х

Dose adjustment	Х	X	X	х	X			
Dispense/High Intensity	х	X	X	х	X	X		
Returns/Drug Account	х	X	X	Х	Х	Х	Х	
Subject reimbursement	х	Х	Х	Х	X	X	Х	

Study Flow Chart

Table of Contents

Synopsis	2
Primary Objective	2
Secondary Objectives	2
Study Duration	2
Study Design	
Study Population	
Number of Participants	
Number of Study Sites	5
Primary Outcome Variables	5
Secondary and Exploratory Outcome Variables	5
Visit Schedule Table	
Study Flow Chart	9
Abbreviations	Error! Bookmark not defined.
Glossary of Terms	Error! Bookmark not defined.
Glossary of Terms 1 - Introduction	Error! Bookmark not defined. 14
Glossary of Terms 1 - Introduction 1.1 Introductory Statement	Error! Bookmark not defined.
Glossary of Terms	Error! Bookmark not defined.
 Glossary of Terms	Error! Bookmark not defined.
 Glossary of Terms	Error! Bookmark not defined. 14
 Glossary of Terms	Error! Bookmark not defined. 14 14 15 15 15 15 15 15
 Glossary of Terms	Error! Bookmark not defined. 14 14 15 15 15 15 15 15 15 15 15 15
 Glossary of Terms	Error! Bookmark not defined. 14 14 15 15 15 15 15 15 15 15 15 15
 Glossary of Terms	Error! Bookmark not defined. 14 14 14 15 15 15 15 17 18 18
 Glossary of Terms	Error! Bookmark not defined. 14 14 14 15 15 15 15 15 15 15 18 18 18 18
 Glossary of Terms	Error! Bookmark not defined. 14 14 15 15 15 15 15 15 18 18 18 18 18 18 19
 Glossary of Terms	Error! Bookmark not defined. 14 14 15 15 15 15 15 15 15 18 18 18 18 18 18 19 20
 Glossary of Terms	Error! Bookmark not defined. 14 14 14 15 15 15 15 15 17 18 18 18 18 18 18 18 18 20 20 20

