3.3.1 Potential Risks

MYDAYIS is a central nervous system (CNS) stimulant indicated for the treatment of Attention Deficit Hyperactivity Disorder (ADHD) in patients 13 years and older. The most common adverse reactions reported in adults were insomnia, decreased appetite, dry mouth, decreased weight, increased heart rate, and anxiety.

The following adverse reactions have been associated with the use of amphetamines.

Cardiovascular: Dyspnea, sudden death. There have been isolated reports of cardiomyopathy associated with chronic amphetamine use.

Central Nervous System: Psychotic episodes at recommended doses, overstimulation, restlessness, euphoria, dyskinesia, dysphoria, headache, tics, fatigue, aggression, anger, logorrhea, dermatillomania, and paresthesia (including formication).

Eye Disorders: Mydriasis.

Gastrointestinal: Unpleasant taste, constipation.

Allergic: Urticaria, rash, hypersensitivity reactions, including angioedema and anaphylaxis. Serious skin rashes, including Stevens - Johnson syndrome and toxic epidermal necrolysis have been reported.

Endocrine: Impotence, changes in libido, frequent or prolonged erections. Skin: Alopecia.

Vascular Disorders: Raynaud's phenomenon.

Musculoskeletal and Connective Tissue Disorders: Rhabdomyolysis.

Risk of taking a placebo

The subject will have periods of taking a placebo and during this time, their symptoms may return and or get worse.

Risk of Safety Clinical assessments

Potential risks associated with obtaining blood samples are minimal but include: slight bruising, swelling, pain, blood clots, and a small risk of infection or a temporary feeling of faintness.

Potential risks associated with an EKG include an initial feeling of coldness when the test material (sticky pads and gel) touches the skin, localized rash or skin irritation from the test material.

Risk of loss of Confidentiality

Possible loss of confidentiality related to urine screens and clinical data obtained during this study is recognized. As a guard against the loss of confidentiality, all information will be stored in locked files, which can be accessed only by members of the research staff for this project.

Patients will be told to take medication once daily in the morning and report if they have any of these effects at each visit.

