6.2.2 Safety/Pregnancy-related policy

Throughout the study, we will monitor subjects for safety and possible pregnancy. During the screening and eligibility period, we will conduct and report, if applicable clinical laboratory results, to include pregnancy testing, ECG readings and the C-SSRS (conducted as needed per clinician discretion) if there are significant clinical findings. We will monitor subjects weekly for abnormal vital signs, adverse events, and concomitant medications. All adverse events results will be tabulated in manuscripts along with significance testing using the appropriate general linear model.

Subjects will be given a pregnancy contact sheet in the event there is a pregnancy. The pregnant woman will be given a pregnancy inform consent to read and sign to allow us to follow-up with the pregnancy until terminated or full term delivery.

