6.2.2.1 Adverse Events Definition and Reporting

Adverse Event

An **adverse event** (AE) is any symptom, sign, illness or experience that develops or worsens in severity during the course of a study. Inter-current illnesses or injuries should be regarded as adverse events. Abnormal results of diagnostic procedures are considered to be adverse events if the abnormality:

- Results in study withdrawal
- Is associated with a serious adverse event
- Is associated with clinical signs or symptoms
- Leads to additional treatment or to further diagnostic tests
- Is considered by the investigator to be of clinical significant

Serious Adverse Event

Adverse events are classified as serious or non-serious. A **serious adverse event (SAE)** is any AE that is:

- Fatal
- Life-threatening
- Requires or prolongs hospital stay
- Results in persistent or significant disability or incapacity
- A congenital anomaly or birth defect
- An important medical event

All adverse events that do not meet any of the criteria for serious should be regarded as **non-serious adverse events**.

Adverse Event Reporting Period

The study period during which adverse events must be reported is normally defined as the period from the initiation of any study procedures to the end of the study treatment follow-up. For this study, the study treatment follow-up is defined as 30 days following the last administration of study treatment.

Preexisting Condition

A preexisting condition is one that is present at the start of the study. A preexisting condition should be recorded as an adverse event if the frequency, intensity, or the character of the condition worsens during the study period.

General Physical Examination Findings

At screening, any clinically significant abnormality should be recorded as a preexisting condition. At the end of the study, any new clinically significant findings/abnormalities that meet the definition of an adverse event must also be recorded and documented as an adverse event.

Post-study Adverse Event

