6.4.3.7 Other

No additional analysis other than what was already discussed will be done.

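### Pulse, blood pressure and weight are scheduled repeatedly, but the supplied plan gives only adverse events an analysis, so the average change in these measures would not be reported

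*Combined protocol and SAP*

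**What the plan says.** Section 3.3.1 lists the known harms: "The most common adverse reactions reported in adults were insomnia, decreased appetite, dry mouth, decreased weight, increased heart rate, and anxiety". Two of the six, heart rate and weight, are continuous measurements.

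The Synopsis visit schedule has a row labelled "Vital Signs w/ HT/WT", marked at screening and at each of Visits 2 to 7. Section 6.4.3.3 states "We will monitor weekly vital signs (temperature, pulse, respiration, and blood pressure"); weight is not in that list.

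On analysis, section 6.2.2 commits to this: "All adverse events results will be tabulated in manuscripts along with significance testing using the appropriate general linear model". Section 6.4.3.3 repeats the commitment in almost the same terms. Both sections say that vital signs are monitored, and neither says how the readings will be summarised. The variable lists in sections 5.1, 6.4.1, 6.4.3.2 and 6.4.4 cover symptom scales, self-report, executive function and neuropsychological tests, and none includes pulse, blood pressure or weight. Section 6.4.3.7 then closes the list: "No additional analysis other than what was already discussed will be done".

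**The concern.** A measurement taken every week and never summarised leaves the paper with one view of these effects: the adverse event table. That table records individual patients whose change someone decided to call an event. It cannot show a modest shift shared by most of the group, with most values still in the normal range.

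The supplied text sets no numeric limit for pulse, blood pressure or weight at which a reading becomes an event. Section 6.2.2.1 relies on consequences (withdrawal, further tests or treatment, associated signs or symptoms) or on the investigator's view of clinical significance. Under section 6.1.4 the study doctor and research staff know whether the patient is on placebo or Mydayis, so that view is not blinded.

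What is at stake is the completeness of the safety report for two effects that the protocol itself expects.

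**Working it through.** **Text check.** The finding rests on the text, so the sections are set side by side first.

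| Step | Where | What it gives |
|---|---|---|
| Expected harm | 3.3.1 | Heart rate and weight named; blood pressure not named |
| Measured | Visit schedule; 6.4.3.3 | Pulse and blood pressure weekly; weight through the schedule row only |
| Analysed | 6.2.2; 6.4.3.3 | Adverse events only |
| Other variable lists | 5.1; 6.4.1; 6.4.3.2; 6.4.4 | No vital sign, no weight |
| Anything further | 6.4.3.7 | Excluded |

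No supplied section leads from the collected readings to a reported mean change.

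**The plan's own figure.** Section 6.4.2 states power of 90% or more for 32 evaluable patients, effect size 0.6, two-sided 0.05, for a baseline-to-endpoint difference. With a paired t-test, noncentrality = 0.6 × √32 = 3.39 on 31 degrees of freedom, and power is 90.8%. The figure reproduces. It concerns efficacy; no figure is given for safety.

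**What the unused readings could show.** The half-width of a 95% confidence interval for a mean paired change is t(0.975, n−1) × SD / √n. For n = 32 this is 2.040 × SD / 5.657 = 0.361 × SD. The SDs of change below are assumptions.

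| Measure | Assumed SD of change | 95% CI half-width, n = 32 |
|---|---|---|
| Pulse | 8 bpm | 2.9 bpm |
| Pulse | 10 bpm | 3.6 bpm |
| Pulse | 12 bpm | 4.3 bpm |
| Weight | 1.5 kg | 0.5 kg |
| Weight | 2 kg | 0.7 kg |
| Weight | 3 kg | 1.1 kg |

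With n = 30, the lower figure that some sections use, the multiplier is 0.373 and the pulse half-widths are 3.0, 3.7 and 4.5 bpm.

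**Why no adverse event count is claimed.** An expected count depends almost wholly on the threshold and the number of visits, and the documents give no threshold. Suppose a true mean rise of 5 bpm.

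- Threshold: a rise of 20 bpm or more. The share of patients is 1 − Φ((20 − 5)/SD) = 3.0%, 6.7% and 10.6% for SDs of change of 8, 10 and 12 bpm. Times 32, that is 1.0, 2.1 and 3.4 patients.
- Threshold: above 100 bpm at one visit, with on-drug mean 80 and SD 10. The share is 1 − Φ(2) = 2.3%, or 0.7 of 32.
- The same threshold crossed at any of Visits 4 to 7, with assumed within-patient correlation 0.5 to 0.7. A simulation gives about 1.9 to 2.3 of 32. With on-drug mean 83 and SD 11 it gives about 4.6 to 5.5.

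The range is too wide to predict what the event table would show. Under none of these thresholds does the count give the mean change.

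**The case against.** The strongest reply is that these harms would still be reported. Section 6.2.2.1 opens with a broad definition of an adverse event that includes any sign that develops or worsens. The narrower conditions, introduced by "Abnormal results of diagnostic procedures are considered to be adverse events if the abnormality", apply to diagnostic procedures. Section 6.2.2 has staff look for abnormal vital signs each week, and the reporting section requires them to ask about events at each contact. A raised pulse or a weight loss in one patient can therefore reach the table. This stands. A reader might infer that the harms would go largely unreported, or that the table would typically show no such event or only one. The documents do not support either inference: the route for individual events is open, and the count cannot be derived. What is lost is the measured average change.

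Other replies stand in part:

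- Sections 6.3 and 6.3.5 say that the Visit 4 to 7 procedures, vital signs included, may be performed, and visits are hybrid. Repeated weight rests on one schedule row. Readings may be missing, so the number measured must be shown.
- The appendix table lists a separate Statistical-Analysis-Plan, which was not supplied. It may already contain such a summary.
- Safety is not a stated objective, section 2.1.2 says that adult safety data come from three randomised placebo-controlled studies, and an uncontrolled change cannot be attributed to the drug. This limits the importance of the point.
- Section 6.4.3.7 may be template wording that was not meant to bar a routine safety table. As written, however, it does bar one.

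**Conclusion.** The point holds in a limited form. In the supplied text, pulse, blood pressure and weight are scheduled repeatedly, two of them correspond to harms listed in section 3.3.1, and no summary of their change is planned or permitted. Individual changes judged to be adverse events would be tabulated and tested, by staff who know the treatment phase; the mean change would not be reported.

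If the SD of pulse change is 8 to 12 bpm and 32 patients are measured, the omitted summary would locate the mean change to within about 2.9 to 4.3 bpm. That figure rests on assumed SDs and on complete readings; missing ones would widen it. The textual finding needs neither assumption, but it is confined to the documents supplied.

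Blood pressure is not among the common reactions in section 3.3.1. It belongs in the same table because it is collected with the others. None of this affects the efficacy analysis. It is a worthwhile, low-cost improvement in reporting.

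**What to change.** In section 6.4.3.3, add weight to the listed measures and state the following:

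- Pulse, systolic and diastolic blood pressure and weight will be summarised at each of Visits 4 to 7 as mean change from Visit 3 (end of placebo lead-in), with 95% confidence interval and number of patients measured.
- The largest on-drug change per patient will also be shown.
- The population is all patients who took at least one dose of Mydayis.
- The results are descriptive within-patient changes without a concurrent control.

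The Visit 2 to Visit 3 change may be shown beside these as context. It covers one week only and is a weak reference for weight over four weeks. A display by dose is best left out. If it is kept, mark it as confounded, because dose follows response and tolerability and rises with time.

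Except this summary from section 6.4.3.7. If the separate Statistical-Analysis-Plan in the appendix table already covers it, make the sections agree.

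The cost is a paragraph and one table. No scheduled visit, measurement or patient is added, and no dosing or stopping rule changes. The downside is one more uncontrolled table, possibly with gaps where visits were remote.

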6.4.3.4 Analysis of Subject Characteristics

All subjects will be entered into the analysis including:

All-randomized population: Any subject randomized into the study, regardless of whether they received study drug

All-treated population: Any subject randomized into the study that received at least one dose of study drug

Protocol-compliant population: Any subject who was randomized and received the protocol required study drug exposure and required protocol processing

6.4.3.5 Interim Analysis

Interim analysis will not be done.

6.4.3.6 Health economic evaluation

Analysis to evaluate heath economic impact, which may include net health benefits, costeffectiveness, cost-utility, and cost benefits of the intervention will not be done.

6.4.3.7 Other

No additional analysis other than what was already discussed will be done.

6.4.4 Subsets and Covariates

Statistical Analysis Plan: Our primary outcome is effects on overall adult ADHD symptoms via total AISRS Score. In secondary analyses, we will also analyze the following variables: Evaluation of ADHD subset IA and HI symptoms on AISRS, TASS 1 hour, 4 hours and 14-15 hours post dose: (total, inattentive and hyperactive-impulsive subsets) (for effects of Mydayis over time at different points of the day and within the day); expanded Adult ADHD Self Report Scale (ASRS) Symptom Checklist (total, inattentive and hyperactive-impulsive, executive function and emotional control subsets); symptoms of executive function (BRIEF-A: GEC, metacognition, behavioral regulation scales and subscales: Inhibit, Shift, Emotional Control, Initiate, Working Memory, Plan/Organize, Organization of Materials, Monitor), and neuropsychological tests (Verbal Interference/Stroop: Color, Word and Interference Score; Go/No-Go: Accuracy, False Negative errors, False Positive errors and Response Time and CPT/TOVA: Response Time

Variability [RVP], Response Time, d', Errors of Omission, Errors of Commission, Post-Commission Response Times, Multiple Responses, Anticipatory Responses).

Our statistical analysis framework will be the general linear regression model. We will choose the distributional family and link function based on the distribution of the outcome variables. Each regression model will predict the outcome as the dependent variable with weeks in trial after the end of the single-blind placebo lead-in as the independent variable. All analyses will use the ITT sample. For our design, a significant effect of week assesses the significance of the drug effect. We have chosen an IIT analyses as we can include all patients except for placebo responders in the analyses. We have chosen a single-blind placebo lead-in to define placebo responders, which are defined as patients who experience \geq 30% decrease in their total AISRS scores during placebo lead-in treatment and will be discontinued from the protocol. We anticipate that, based on the literature, 10% or fewer of patients will be placebo responders and that the overall discontinuation rate in the trial will be 20%. Changes within the day in TASS ratings 1 hour post dose vs. 4 hour post dose vs. 14-15 hours post dose will also be analyzed via the general linear regression model. Correlations between ADHD and executive function ratings will be examined via Spearman's correlation coefficients.

Exploratory Objectives: We will explore correlations of TASS ratings with AISRS ratings to examine overall ADHD ratings vs. ADHD ratings throughout the day. We will also explore correlations of changes in neuropsychological assessments of executive function (WEBNEURO; STROOP, GO/NO-GO, CONTINUOUS PERFORMANCE TEST) versus changes in BRIEF-A measures. Furthermore, we will examine potential differential effects of Mydayis in the sample of patients who have defined executive dysfunctions (GEC score on BRIEF- A >= 65 at placebo-baseline). We will also examine correlations in self-report of ADHD symptoms on the ASRS) versus clinician report of ADHD symptoms on the ASRS versus these measures of executive function and emotional dyscontrol on the ASRS versus these measures on the BRIEF-A.

6.4.5 Handling of Missing Data

Missing outcome data will be handled in regards to analysis in the following way: last observation will be carried forward.

7 - Trial Administration

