4.3 Secondary Objectives

The secondary objectives of this study are to examine the changes after Mydayis treatment in:

1. Overall inattentive (IA) and hyperactive-impulsive (HI) ADHD symptom subsets on the AISRS and overall impairment via the Clinical Global Impression-Severity (CGI-S) scale.

2. Total ADHD symptoms fourteen to fifteen hours after AM dosing as measured via total scores on the Time Sensitive Adult ADHD Symptom Scale (TASS) and the Inattentive (IA) and hyperactive- impulsive (HI) ADHD symptom TASS subsets.

3. Neuropsychological measurement of executive function in the early evening (fourteen to fifteen hours after morning dosing) as measured by (WebNeuro: Verbal Interference/Stroop, Go/No-Go, CPT/TOVA)

4. Clinical symptoms of executive function, as measured by the BRIEF-A.

5 - Study Design

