Participants with \geq 30% decrease in total AISRS scores from Visit 1 to Visit 2 will be considered placebo responders and discontinued from the study.

All other participants will be prescribed 12.5mg of Mydayis. They are instructed to take the study medication once daily at 5 am in the morning and to return all unused medication at the next study visit. The TASS will be done three times on days of administration: V1, V3, V4, V5, V6, and V7. The recommended dosing is at 5 am +/- 1 hour. The first TASS will be done at half hour to one-hour post dose (5:30 to 6 am +/- 1 hour), the second TASS will be done 4 hours post dose (9am +/- 1 hour) and the third TASS will be done 14-15 hours post dose(7pm+/- 1 hour). All TASS administrations will be via telephone.

Treatment Phase

MYDAYIS Treatment Phase (Week 1-4, Visit 4-7)

Participants will return to the study site every 7 days during the MYDAYIS treatment phase. The following procedures and assessments may be performed at Visits 4-7: vital signs, AISRS, CGI-S, TASS, Expanded ASRS, C-SSRS, Concomitant medications and AEs, if any, will be noted and drug accountability and compliance will be performed. Note: WebNeuro battery and BRIEF-A assessments are done only at Visit 7.

Participants must take 80% of the prescribed doses of study medication in order to be considered compliant The TASS will be done three times on days of administration. The recommended dosing is at 5 am +/- 1 hour. The first TASS is done at half hour to one-hour post dose (5:30 to 6 am +/- 1 hour), the second TASS is done 4 hours post dose (9am +/- 1 hour) and the third TASS is done 14-15 hours post dose (7pm+/- 1 hour). All TASS administrations will be via telephone.

Subjects will receive a re-supply of study medication at the end of every visit during the Mydayis treatment phase. The dose of Mydayis can be clinically adjusted (in the judgement of the investigator) starting at Visit 4 in 12.5mg increments based upon clinical response and side effects, up to a maximal dose of 37.5 mg/day. Participants will be instructed to return all unused medication at each study visit.

Withdrawal/End of Treatment (Visit 7)

Participants will return to the study site for Visit 7 within 7 days of Visit 6. The following procedures and assessments will be performed at Visit 7: vital signs, AISRS, CGI-S, WebNeuro battery assessments, TASS, Expanded ASRS, C-SSRS and BRIEF-A.

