MYDAYIS Treatment Phase (Weeks 1-4, Visits 4-7): takes approximately two hours.

Participants will return to the study site every 7 days during the MYDAYIS treatment phase. The following procedures and assessments may be performed at Visits 4-7: vital signs, AISRS, CGI-S, WebNeuro battery assessments (Verbal Interference/Stroop, Go/No-Go, CPT/TOVA), TASS, Expanded ASRS, C-SSRS and BRIEF-A. Note; Webneuro and Brief-A only done on visit 7.

Concomitant medications and AEs, if any, will be noted and drug accountability and compliance will be performed. Participants must take 80% of the prescribed doses of study medication in order to be considered compliant.

The TASS will be done three times on days of administration. The recommended dosing is at 5 am +/- 1 hour. The first TASS is done at half hour to one hour post dose (5:30 to 6 am +/- 1 hour), the second TASS is done 4 hours post dose (9am +/- 1 hour) and the third TASS is done 14-15 hours post dose (7pm+/- 1 hour). All TASS administrations will be via telephone.

Participants will receive a re-supply of study medication at the end of every visit during the Mydayis treatment phase. The dose of Mydayis can be clinically adjusted (in the judgment of the investigator) starting at Visit 4 in 12.5 mg/day increments based upon clinical response and side effects, up to a maximal dose of 37.5 mg/day. Participants will be instructed to return all unused medication at each study visit.

Withdrawal/End of Treatment (Visit 7): takes approximately two and a half hours.

Participants will return to the study site for Visit 7 within 7 days of Visit 6. The following procedures and assessments will be performed at Visit 7: vital signs, AISRS, CGI-S,

WebNeuro battery assessments (Verbal Interference/Stroop, Go/No-Go, CPT/TOVA), TASS, Expanded ASRS, C-SSRS and BRIEF-A.

Concomitant medications and AEs, if any, will be noted and drug accountability and compliance will be performed. Participants should report taking at least 80% of the prescribed study medication in order to be considered compliant.

The TASS will be done three times on days of administration. The recommended dosing is at 5am +/- 1 hour. The first TASS is done at half hour to one hour post dose (5:30 to 6 am +/- 1 hour), the second TASS is done 4 hours post dose (9am +/- 1 hour) and the third TASS is done 14-15 hours post dose (7pm+/- 1 hour).

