6.4.3 Planned Analyses

6.4.3.1 Primary Analyses

Our statistical analysis framework will be the general linear regression model. We will choose the distributional family and link function based on the distribution of the outcome variables. Each regression model will predict the outcome as the dependent variable with weeks in trial after the end of the single-blind placebo lead-in as the independent variable. All analyses will use the ITT sample. For our design, a significant effect of week assesses the significance of the drug effect. We have chosen an IIT analyses as we can include all patients except for placebo responders in the analyses. We have chosen a single-blind placebo lead-in to define placebo responders, which are defined as patients who experience \geq 30% decrease in their total AISRS scores during placebo lead-in treatment and will be discontinued from the protocol. We anticipate that, based on the literature, 10% or fewer of patients will be placebo responders and that the overall discontinuation rate in the trial will be 20% (*Manor et al. 2012*). The changes within the day in TASS ratings, 1-hour post dose vs. 4 hours post dose vs. 14-15 hours post dose will also be analyzed via the general linear regression model. Correlations between ADHD and executive function ratings will be examined via Spearman's correlation coefficients.

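### The carry-forward rule is not defined for the three daily TASS ratings, and either way of reading it gives a biased fill for a missed 14-15 h rating

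*Combined protocol and SAP*

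**What the plan says.** Section 6.4.5 is a single sentence: "Missing outcome data will be handled in regards to analysis in the following way: last observation will be carried forward". It covers every outcome and does not define the last observation by time of day, visit or scale.

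Section 6.3.5 sets the TASS schedule: "The TASS will be done three times on days of administration". The first rating comes within an hour of dosing, then "the second TASS is done 4 hours post dose (9am +/- 1 hour"), and "the third TASS is done 14-15 hours post dose (7pm+/- 1 hour"). For most visits the section adds "All TASS administrations will be via telephone", and Section 7.8 says that subjects are called three times a day.

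The evening rating carries an objective of its own. Section 4.3 lists as the second secondary objective "Total ADHD symptoms fourteen to fifteen hours after AM dosing as measured via total scores on the Time Sensitive Adult ADHD Symptom Scale (TASS"). Section 6.4.3.1 also plans a within-day analysis: "The changes within the day in TASS ratings, 1-hour post dose vs. 4 hours post dose vs. 14-15 hours post dose". Section 6.4.3.2 lists the three times as separate TASS variables, and Section 6.4.3.1 regresses each outcome on week after the placebo lead-in.

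**The concern.** Whether the effect lasts into the early evening is the question in the trial's title. The 14-15 h TASS is the symptom rating tied to that hour. Because each rating is a separate telephone call, the 7 pm call can be missed when the morning calls were made. The analyst then has to decide which observation is the last one, and Section 6.4.5 does not say.

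There are two natural readings. In time order, the last observation is the same day's 4 h rating. Within a time slot, it is the previous visit's evening rating. The first imports a morning score into the evening outcome. The second imports a score from another week, when the treatment or dose may have been different. Neither estimates the missing evening score, and both enter the model as if they had been observed.

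**Working it through.** **The plan's own figure.** The plan gives no number on this point. Its power statement (32 evaluable patients, effect size 0.6, two-sided 0.05, at least 90%) reproduces as 90.8% with a paired t test. It concerns the baseline-to-endpoint comparison and has no bearing on the fill.

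**Inputs.** From the documents: three ratings per assessment day (Section 6.3.5), 32 evaluable patients and two-sided 0.05 (Section 6.4.2). Assumed, because the documents give no values: the share m of evening calls missed, the 4 h effect E4 and the evening effect E14. Effects are in SD units. The values 0.6 and 1.2 for E4 are borrowed from the effect sizes in Section 6.4.2 for illustration only.

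**Reading 1: same-day carry, calls missed at random.**

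- A filled patient-day has a 4 h to 14-15 h change of exactly 0, so estimated waning = (1-m) × true waning. At m = 10%, 20% and 30%, the estimate loses 10%, 20% and 30% of the waning.
- Estimated evening effect = (1-m) × E14 + m × E4, so bias = m × (E4 - E14). This needs either the same missed-call rate on placebo days, or equal placebo-day scores at 4 h and in the evening.

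| E4 | E14 | m | Evening estimate | Bias |
|---|---|---|---|---|
| 0.6 | 0.3 | 20% | 0.8 × 0.3 + 0.2 × 0.6 = 0.36 | +0.06 |
| 0.6 | 0 | 10% | 0.1 × 0.6 = 0.06 | +0.06 |
| 0.6 | 0 | 20% | 0.2 × 0.6 = 0.12 | +0.12 |
| 1.2 | 0 | 20% | 0.2 × 1.2 = 0.24 | +0.24 |
| 0.6 | 0.6 | 20% | 0.8 × 0.6 + 0.2 × 0.6 = 0.60 | 0 |

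A simulation (32 patients, 20,000 runs, assumed within-day correlation 0.5) agrees with these means. With no true evening effect and m = 20%, the chance of declaring one is about 10% when E4 = 0.6 and about 21% when E4 = 1.2, against a nominal 5%.

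**Reading 2: previous visit, same time slot.** Bias = m × (E14 at the previous visit - E14 at this visit).

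- Visit 4 takes the Visit 3 value, from the placebo lead-in, where the effect is 0. With E14 = 0.3 and m = 20%, bias = 0.2 × (0 - 0.3) = -0.06, and the estimate is 0.24.
- Later visits take a value from a week when the dose may have differed. The documents do not fix the size of that bias.

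**Does using observed ratings only remove the bias?** Assume 32 patients, true waning of 4 points, SD of the change 8, and 20% of evening calls missed. The entries are estimated waning divided by true waning.

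| Missed calls | Same-day fill | Observed pairs only |
|---|---|---|
| At random | 0.80 | 1.00 |
| More likely when the evening is worse (logistic, slope 1 per SD) | 0.52 | 0.65 |

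Dropping the fill removes the bias in the first case. In the second it reduces the bias but leaves a good part of it.

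**The case against.** The strongest reply is that the plan never says ratings are carried within a day. The three TASS times are listed as separate variables and each outcome is modelled on week, so carrying within a time slot fits the text at least as well. That stands. A reader might infer that the plan scores every missed evening call as full persistence of effect; the documents permit that reading but do not state it.

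The direction of bias is not fixed either. It favours the duration claim only under the same-day reading and only if the effect is larger at 4 h than in the evening. Section 2.1.2 cites earlier studies with an effect up to 16 h; if that holds here, the same-day fill does no harm. If the 4 h call is missed too, the rating from the first hour is carried. On the PERMP data in Section 2.1.2, separation from placebo began at 2 h or 4 h, so that fill would tend to work against the drug. With no concurrent placebo, a within-day change also mixes waning with ordinary time-of-day variation.

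A reader might also infer that the fill costs power to detect waning. It does not: in the scenario above, observed pairs alone give practically the same power as the filled data. The loss comes from the missed calls.

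The planned 20% discontinuation rate is no guide to m, since a patient who has left misses all three calls. Finally, the appendix list names a separate Statistical Analysis Plan whose text was not available, and it may define the rule.

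None of this rescues the rule as written. Both readings give a poor fill, and the choice between them is left open.

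**Conclusion.** The point holds as a gap that should be fixed. Section 6.4.5 applies carry-forward to a scale rated three times a day without defining it, and neither available reading estimates the missing evening score. The same-day reading understates waning by the share of calls missed. It overstates the evening effect by 0.06 to 0.24 SD in the waning examples shown and by nothing if the effect fully persists. The same-slot reading biases against the drug at Visit 4 and in an unknown direction later. These sizes rest on assumed missed-call rates and effects, and on the placebo-day condition stated with the formula.

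The consequence falls on the second secondary objective and the within-day comparison. A reader might infer that the main efficacy result is compromised. The AISRS total, named as primary in Sections 4.2, 5.1 and 6.4.4, has no within-day ratings and is not touched by the within-day fill. Section 6.4.1 instead names TASS-AISRS correlations as primary, and filled TASS values would enter those; that conflict over the primary outcome is a separate matter.

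**What to change.** In Section 6.4.5, state that TASS ratings are never carried from one time of day to another or from one visit to another. Analyse all observed TASS ratings in one repeated-measures model with week, time of day, their interaction and a patient random effect. Report the number of missed calls at each time point. Add a sensitivity analysis for evening calls missed because symptoms are worse, since the observed-data model reduces that bias without removing it. If the separate Statistical Analysis Plan has a rule for this, bring the two texts into line.

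The cost is a short wording change, a little more programming and slightly wider intervals than filled data would show.
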